Incarceration: This is a minimal risk study that recruits non-prisoner patients from substance abuse treatment programs. However, a portion of the study patients are likely to be incarcerated during the study period due to illegal activities that are common in this population. If a patient is incarcerated during study participation, all study procedures are suspended except the evaluations. In the ICF, patients indicate whether or not they would like the evaluation questionnaires sent to them in prison. The mailing delivered to the incarcerated patient only contains the evaluation questionnaires and a cover letter indicating the questionnaires are follow-up to a study the patient participated in at UConn Health. A stamped and addressed return envelope is also provided with the questionnaires. If the patient completes and returns the questionnaires for Month 3 and 6, they will receive \$25 in the form of a check. The patient will receive the check after their release from incarceration or they may designate a person to whom the check should be sent during their incarceration. The patient is notified in the ICF that their participation in this study while incarcerated will have no effect on their eligibility for parole.

Compensation: To compensate for their time, participants will be given a \$50 giftcard for the baseline interview and \$100 in their choice of a check or giftcard for each subsequent interview. Participants in the control group will be compensated \$5 (check or giftcards) for each urine sample they provide during the treatment phase (i.e., two samples per week for ten weeks). Participants who travel to UConn for their study visits will be provided with \$15 (check or giftcards) to cover the cost of travel (bus passes, gas, parking, etc). Participants may also earn up to \$45 for eligible referrals (\$15 each, up to 3 referrals).

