Random Assignment occurs after the BL evaluation. A computerized urn randomization procedure (Stout et al., 1994) will balance patients on gender and submission of a positive sample for any illicit drug (i.e., cocaine, amphetamine, methamphetamine, opiate, benzodiazepine, or marijuana) at baseline, because positive samples at treatment initiation are related to poor outcomes (Preston et al., 1998; Silverman et al., 1998; Stitzer et al., 2007). Prior to randomizing participants, up to 10 pilot participants will complete a pilot study consent form and study procedures described for Group B below, through month 3 follow-up, for the purpose of monitoring staff on study procedures prior to the randomized trial.

Group A (Standard care [SC]; n=20) patients will receive SC at the substance use clinic where they are seeking treatment. This treatment approach typically consists of group therapy sessions, including daily planning, 12-Step treatment, relapse prevention, coping and life skills training, and AIDS education. Groups are led by recovering individuals, nurses, and masters level counselors. Very few individual sessions are provided at these clinics, and then only in cases of emergencies (e.g., suicidality). These clinics rarely conduct breathalyzers or urine testing for illicit drug use. Any such testing will occur as it normally would, and study procedures will not

impact standard care in any way. If the participant is not already enrolled in SC at a substance use clinic, they will be provided with referrals to clinics convenient to their home.

Study urine samples will be collected twice weekly. Patients will receive a \$5 payment (check or gift cards) for each of 20 urine/breath sample submissions during weeks 1-10. In addition, they will be asked to complete the NSSEP-SS and the CES-D to assess PTSD symptoms and depression weekly. If patients cease attending groups, they will still be encouraged to attend these brief meetings for sample monitoring. To maintain consistency with standard care in these clinics, results from toxicology screens will not be discussed with providers.

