The prize bowl contains 500 cards; 50% are winning and the remainder are non-winning (i.e., "Good Job"). The majority (209/500) of winning cards are small prizes (about \$1 in value; e.g., small toiletries, food items); 40/500 cards are large prizes (up to \$20 in value; e.g., small electronics, gift cards). One card (1/500) is a jumbo prize (up to \$100 in value; e.g., MP3 players/iPod). The maximum number of draws is 132, with an expected average maximum earned per person of about \$255 over 10 weeks. Slips are drawn consecutively (without replacement) within session and then replaced between sessions. This reinforcement approach has been used successfully in other treatment trials (Petry et al., 2004; 2005). Prize CM is equally effective as voucher CM (Petry et al., 2005) and it is more cost-effective than voucher CM (Olmstead & Petry, 2009).

At week 1, participants will earn 1 draw for the first negative sample and the number of draws will increase by 1 draw for each consecutive negative sample up to a cap of 8 draws. Once the cap of 8 draws is achieved, participants will continue to receive 8 draws for each consecutive negative sample. No draws are earned for positive samples, unexcused absences (e.g., no shows), or refused samples, and these events will reset the schedule to 1 draw for the next negative sample and escalation will resume as described above. Excused absences (e.g., court appearance, doctor's appointment) will be accommodated with valid proof and will not reset the reinforcement schedule.

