It is expected that, for some emerging adults, marijuana will be their drug of choice. Marijuana treatment requires a different CM schedule, as marijuana can continue to be detected on urine drug screens for up to 3-4 weeks following last use among heavy marijuana users. In these cases, participants will earn 1 draw simply for attending sessions and providing a urine sample for the first 4 weeks of CM treatment. Once the participant is able to provide a negative screen, they will begin to earn escalating rewards starting at the same level as their peers who are in treatment for other illicit drugs. For example, if a participant is positive for marijuana until week 3, s/he would receive one draw for each session attended leading up to the negative screen and then 5 draws for his/her negative urine drug screen in week 3. Once the participant tests negative for marijuana (or the 4 weeks has elapsed), s/he is subject to the same rules for negative and positive screens as other participants.

This adaptation allows us to engage marijuana users in the CM treatment process during the time that they are waiting for their urine drug screens to reflect their abstinence.

Prolonged Exposure Therapy. Participants in Group B will also engage in Prolonged Exposure (PE) therapy for the treatment of PTSD. PE is a well-established treatment for PTSD for a wide range of populations, including victims of sexual and/or physical assault, childhood trauma, accidents, and war veterans. A 2010 meta-analysis reviewed 13 randomized controlled trials evaluating PE over 20 years and concluded that this treatment approach "is a highly effective treatment for PTSD, resulting in substantial treatment gains that are maintained over time" (Powers, Halpern, Ferenschak, Gillihan, & Foa, 2010). PE has also been evaluated with patients who have co-occurring PTSD and substance abuse disorders, resulting in evidence for its safety, feasibility, and efficacy with this patient population (Brady, Dansky, Back, Foa, & Carroll, 2001; Foa et al., 2013; Mills et al., 2012).

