Feasibility measures relevant to recruitment and dropout proportions will be examined with 95% confidence intervals used to estimate the proportion of emerging adults who agree to participate out of the number deemed eligible and to compare those who complete versus do not complete the intervention. Feasibility will be evaluated by examining therapist adherence using ratings of taped sessions as well as emerging adults' responses to qualitative interviews. Measures of safety will include repeat trauma exposure, suicidal ideation, and risky substance use behaviors. Patterns of safety indicators will be examined using frequency distributions and descriptive statistics. In addition, rates of these indicators will be compared across Group A and Group B to determine if there is any increased risk posed by the active treatment compared to treatment as usual. These data will be used to make any necessary protocol changes.

Aim 3: To conduct a preliminary analysis of the efficacy of the integrated protocol in improving symptoms among emerging adults.

Groups will be compared with respect to the primary outcome variables (substance use, PTSD symptoms) and secondary variables (delinquent behaviors, depression, adaptive functioning, HIV risk behaviors). An important issue preceding analyses is to identify baseline differences between groups despite random assignment. Differences between groups that may be related to outcome will be used as covariates or fixed factors, as appropriate. We will conduct intent-to-treat analyses, with all randomized patients and apply random regression models, also known as hierarchical linear models (HLM), to determine if patients improve differentially between groups over time (Raudenbush & Bryk, 2002). HLM is specifically designed for repeated measures designs with missing data, allowing for intra-subject serial correlation and unequal variance and covariance structures over time by incorporating available trend data for each individual with information on the group from which the subject is drawn. Maximum likelihood estimation enables analyses to be performed for the full trial without having to drop subjects with incomplete data, and both continuous and dichotomous variables can be analyzed. If data cannot be normalized, group by time effects will

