be assessed with HLM, coding patients as improved or not at each time point. The main analyses will focus on during treatment effects (baseline through follow-up) but long-term effects (baseline to 3-month post-treatment follow-up) will also be analyzed (see follow-up section).

The primary outcomes are substance use is longest duration of abstinence from illicit drug use and symptoms of PTSD (NSESP-SS), continuous variables that can be transformed if needed. The primary substance use outcome is longest duration of abstinence from substances (LDA), the main outcome variable in most CM trials and the variable most strongly associated with long-term abstinence (Higgins et al., 1994, 2000, 2003; Petry et al., 2005). Linear regression will evaluate group differences in LDA, with condition as the independent variable (along with any important covariates). If data cannot be normalized, nonparametric tests will be used. While LDA is the primary substance use outcome measure, it is affected by retention as missing samples break a string of abstinence (unless preceded and followed by negative samples, and an excused 'miss' is obtained due to documented illness, court appearances, etc. usually comprising <5% of missed samples). Proportion of negative samples, in contrast, is unaffected by missing samples. Thus, we will also analyze proportion of samples negative for substances as a secondary outcome using similar analyses.

Analyses will focus on the 10-week during treatment effects, but long-term effects will also be analyzed. These will involve logistic regressions to predict substance abstinence at the 3-month follow-up, with treatment group and any important baseline characteristics (e.g., baseline sample result) included as independent variables. HLM analyses for dichotomous measures will also be conducted to evaluate substance abstinence over time between treatments from baseline throughout the 3-month follow-up. Additional secondary drug use outcomes will investigate abstinence from all substances concurrently and from each of the other drugs independently. These analyses will parallel those outlined above.

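### Proportion of negative samples is untouched by missing samples only arithmetically; the arms compare fairly only if submission depends on the result alike in both, and their incentives to submit differ

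*Combined protocol and SAP*

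**What the plan says.** Data Analysis Strategy, Aim 3, makes LDA the primary substance use outcome and discloses its weakness: "it is affected by retention as missing samples break a string of abstinence", unless the miss is excused and lies between negatives. It then says of the secondary outcome: "Proportion of negative samples, in contrast, is unaffected by missing samples". That outcome is to be analysed like LDA, by regression on condition with one value per person. The same section states: "We will conduct intent-to-treat analyses, with all randomized patients". It does not write out the denominator, and it gives no rule for a participant who submits nothing.

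The incentives to submit are set elsewhere. Group A receives $5 "for each of 20 urine/breath sample submissions during weeks 1-10", and the Compensation paragraph ties this to giving the sample, not to its result. If Group A members stop attending groups, "they will still be encouraged to attend these brief meetings for sample monitoring". For Group B, the Contingency Management Component says: "No draws are earned for positive samples, unexcused absences (e.g., no shows), or refused samples". All of these events also reset the schedule to 1 draw. The exception is for participants whose drug of choice is marijuana: "participants will earn 1 draw simply for attending sessions and providing a urine sample for the first 4 weeks of CM treatment".

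**The concern.** A proportion of submitted samples does not fall when someone misses a visit, but it does depend on which samples are missing. If participants who expect a positive tend to stay away, the observed proportion rises. If they do so more in one arm, a difference appears without any effect of treatment. The protocol gives a reason to expect this. An expected positive is worth $5 in Group A and, outside the marijuana schedule, nothing in Group B, which is no more than staying away.

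The outcome was added to offset LDA's dependence on retention, so a reader may take agreement between the two as reassurance. The pilot data are also meant to support an application for a larger trial.

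Two scoring gaps need no assumption about behaviour. The proportion is undefined for anyone with no samples, despite the intent-to-treat commitment. And a participant who leaves after 4 negatives of 4 scores 100%, above a completer with 16 of 20 (80%).

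**Working it through.** **The plan's own figures.** None supports the sentence, and the documents give no submission rates or significance level for this outcome. The related figure is the draw schedule: 1 + 2 + ... + 8 = 36, then 12 × 8 = 96, total 132. This matches the stated maximum and confirms 20 scheduled samples in Group B, as in Group A.

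**Incentive per sample.** Group A: $5 for either result, so at most 20 × $5 = $100. Group B: the stated $255 over 132 draws is about $1.93 per draw. A negative (1 to 8 draws) is therefore worth about $1.93 to $15.45, and a positive $0.

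**Formula.** Let p be a person's true share of negatives, and s_neg and s_pos the shares of negatives and positives that are submitted. Then

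observed proportion = p·s_neg / (p·s_neg + (1 − p)·s_pos).

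The observed odds are the true odds times s_neg/s_pos. With no effect, the arms agree only if s_pos/s_neg is equal in both.

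**Size under assumed rates.** Assumptions: no true effect, true negatives averaging 50%, 20 per arm, 20 samples each. Group A submits 80% of all samples, and Group B submits 80% of negatives but fewer positives. If everyone had p = 0.5, Group B at 60% of positives would show 0.40/(0.40 + 0.30) = 57.1% against 50%. Spread between people shrinks this, because those nearly always negative or positive hardly move. For p uniform and r = s_pos/s_neg, the mean is 1/(1 − r) − r·ln(1/r)/(1 − r)². At r = 0.75 this is 4 − 12 × 0.2877 = 0.548, or +4.8 points. Simulated null trials, tested two-sided at an assumed 5% level, agree:

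| Group B submits, of positives | Gap | Everyone at 50% | Mean difference over three spreads, Beta(½,½) to Beta(3,3) | False positives |
|---|---|---|---|---|
| 70% | 10 | +3.3 | +1.6 to +2.9 | 5-7% |
| 60% | 20 | +7.1 | +3.6 to +6.1 | 6-14% |
| 40% | 40 | +16.7 | +8.7 to +14.5 | 11-52% |

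If the pattern is swapped (Group A 60% of positives, Group B 80%), the difference is −5 to −6 points under the uniform and Beta(3,3) spreads.

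**Marijuana schedule.** Take the 40% row, with positives in the first 8 samples submitted at 80%. The difference falls to +9 to +11 points if half of Group B qualify and to +6 to +7.5 if all do (uniform and Beta(3,3) spreads). If all qualify, the first 8 samples are positive and 10 of the other 12 are negative, it is 8.0/(8.0 + 6.4 + 0.8) = 52.6%, or +2.6.

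**Does counting missing as not negative cure it?** Over 20 scheduled samples the expected proportion is p·s_neg, so s_pos drops out. In the 60% and 40% rows the arms agree (0.40 against 0.40), and both this version and LDA stay near 5% false positives. If Group B submits 90% of negatives and Group A 80%, it is biased in turn: 0.45 − 0.40 = +5 points.

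**Does equal overall submission clear it?** No. Let Group A submit 75% of everything, and Group B 90% of negatives and 60% of positives, so 0.5 × 0.90 + 0.5 × 0.60 = 75%. Then, under the uniform and Beta(3,3) spreads:

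| Measure | Difference | False positives |
|---|---|---|
| Over submitted | +7 to +8.5 points | 11-22% |
| Over scheduled | 0.45 − 0.375 = +7.5 points | 15-23% |
| LDA | +0.7 to +1.1 samples | 17-18% |

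**The case against.** The sentence contrasts two scoring rules: a missed sample breaks an LDA string and does not enter a proportion. Read that way it is correct. The plan does not claim an unbiased comparison, and it does not say that agreement with LDA counts as support. This stands, and it is why the remedy is mainly wording and reporting.

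The incentive contrast is also incomplete. Group B gives samples at therapy visits, and a missed second weekly session prompts a phone call. The Compensation paragraph offers $15 travel money to those who come to UConn for study visits, with no condition on arm or result. If treatment sessions count as study visits, which is unclear, some of Group B are paid for attending whatever the result. The marijuana schedule works the same way for a time. All of these could shrink or reverse the bias, and none shows that submission is alike in the two arms.

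LDA remains the primary outcome and penalises missed samples. In the 4-of-4 example the leaver scores 4. The completer's 16 negatives fall into at most five runs, so the longest is at least 4. Timeline Follow-back and the optional most-conservative-index rule (Data Quality Control) are other checks on use, but they do not correct this proportion. The missing-data condition in Aim 3 is stated for the PTSD scale only.

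A reader might also infer from the 12-week cap under Missed Sessions that the denominator could be 24 samples. The documents do not support that for the main analysis: Aim 3 focuses on 10 weeks, and 132 draws correspond to 20 samples (24 would give 132 + 4 × 8 = 164).

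**Conclusion.** The point holds as a minor one. The claim that missing samples leave this outcome unaffected is right about the arithmetic and too strong for a comparison between arms, because the protocol rewards submission differently in each. Under the assumptions above, gaps of 10, 20 and 40 points in submitting positives produce false differences of about 2-3, 4-6 and 9-15 points. The actual size is unknown, since the documents give no submission rates. The false-positive rates further assume a 5% test that the plan does not state.

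Two stronger readings are tempting. One is that the outcome is biased in favour of Group B. That is the likely direction, not an established one, and the sign can reverse. The other is that selective submission of positives would mislead both LDA and the proportion. With equal submission of negatives LDA stays near 5%. Both show a false benefit in the settings where Group B also submits more of its negatives, a retention-type weakness that the plan already discloses for LDA.

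Severity is minor: this is a secondary outcome in preliminary analyses of 40 people.

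**What to change.** 1. Reword the sentence to say that missing samples are not scored positive, but that the comparison depends on submission behaving alike in both arms. State that the denominator is samples submitted, and how participants with none are handled under intent-to-treat.
2. Report scheduled, submitted, excused and missed samples by arm.
3. Add a sensitivity analysis over the 20 scheduled samples in the 10-week window, with missing counted as not negative. Call it a sensitivity check, not an unbiased correction, because it is biased if the arms submit different shares of their negatives.
4. Do not treat agreement between LDA and the proportion as independent support when submission differs by arm. Note that similar overall submission is necessary for that reading but not sufficient.

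The cost is some wording, one table and one more regression, with no change to procedures or payments. The downside is that no version of the outcome is free of bias, so the results will still need a cautious reading. A two-sided range (one arm over scheduled samples, the other over submitted, and the reverse) is optional; with 20 per arm it would be too wide to add much.

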Aim 3: To conduct preliminary analyses exploring whether emerging adults who receive the intervention demonstrate improvement in key symptom domains. Specifically, 40 youth will be randomized to either the integrated treatment or standard care. Primary outcomes will include substance abuse and PTSD. Secondary outcomes will include criminal justice involvement, adaptive functioning, and other mental health symptoms.

The results of the study will have a **significant impact on public health** by informing treatments for co-occurring SUD/PTSD among justice-involved transition age youth, a group at the highest risk for these problems. Demonstrating the efficacy of an integrated treatment approach will provide a valuable clinical tool for community-based therapists to employ in the context of existing evidence-based treatments. Further, should compelling indications of efficacy be found and safety and acceptability be established, these aims will position the research to advance to an appropriately powered randomized controlled trial.

A. SIGNIFICANCE

Prevalence and consequences of substance use problems among emerging adults. Transition age youth (i.e., emerging adults, ages 18-25) represent the age group with the **highest rates of initiation of substance use, increases in substance use, and progression of substance use into substance use disorders** (Chassin, Flora, & King, 2004; Delucchi, Matzger, & Weisner, 2008; SAMHSA, 2009). Substance use plays a significant role in many serious problems during this developmental period, including suicide (SAMHSA, 2010), automobile accidents (Hingson, Heeren, Winter, & Wechsler, 2005), and other lethal events. Emerging adults with SUDs also have increased rates of risky sexual behavior, increasing their chances of contracting HIV and other STDs (King, Nguyen, Kosterman, Bailey, & Hawkins, 2012). Further, SUDs significantly impede successful negotiation of important developmental tasks of this transitional age, leading to increased rates of unemployment and job instability and decreased college attendance (Bray et al., 2000; Mangione et al., 1999). Finally, emerging adults with SUDs represent a greatly underserved population, with a high likelihood of “slipping through the cracks” as they transition from child to adult substance use service providers ([name], Green, & Hoffman, 2009). **Thus, this group has a very high potential to present significant short- and long-term costs for individuals, families, and society.**

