Group B (SC + PE/CM Treatment; n=20) patients will receive the same SC groups as Group A. If they are currently enrolled in substance use treatment, they will continue with that treatment. If not, they will be provided with referrals for substance use treatment in the community. In addition, they will participate in an integrated Contingency Management (CM) and Prolonged Exposure (PE) treatment protocol described subsequently. Either the PI ([name]) or [name], will serve as the study therapist for participants randomized to group B. For cases where [name] serves as the therapist, [name] will provide clinical supervision of study cases.

As in Group A, participants will undergo testing twice weekly with a breathalyzer and urine drug screen. In addition, during the first meeting of the week, participants will engage in both CM and PE components of treatment (described below). During the second meeting of the week, participants will engage in CM and a brief check-in on the components of PE that the participant is working on for homework that week but no new PE-related components will be introduced.

Contingency Management Component. Participants in Group B will participate in CM to target abstinence from substance use. In prize CM protocols, participants earn opportunities to draw cards from a prize bowl. The cards differ in prize value, ranging from \$0 to \$100 in value, and participants can earn increasing numbers of draws with consecutive performance. The variable reinforcement amount feature of prize CM distinguishes it from other reinforcement systems such as voucher CM. Participants will be allowed to draw from the prize bowl if their urine drug screen is negative for opiates, methadone, cocaine, amphetamines, methamphetamines, and marijuana (see additional information about marijuana use below) and their breath screen is negative for alcohol.

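### Follow-up abstinence: logistic regression at N = 40 with uncapped covariates, no small-sample method and no rule for missing outcomes

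*Combined protocol and SAP*

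**What the plan says.** Aim 3 of the Data Analysis Strategy describes the long-term analyses: "These will involve logistic regressions to predict substance abstinence at the 3-month follow-up". On the content of that model, the plan says it is fitted "with treatment group and any important baseline characteristics (e.g., baseline sample result) included as independent variables". One covariate is named, as an example. A general rule under the same aim can add others: "Differences between groups that may be related to outcome will be used as covariates or fixed factors, as appropriate". Neither sentence lists or caps them.

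The sample is small: "40 youth will be randomized to either the integrated treatment or standard care". The arm sizes are given as "Group A (Standard care [SC]; n=20) patients will receive SC" and "Group B (SC + PE/CM Treatment; n=20) patients will receive the same SC groups as Group A". Under Random Assignment, the urn procedure "will balance patients on gender and submission of a positive sample for any illicit drug" at baseline.

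Aim 3 also states "We will conduct intent-to-treat analyses, with all randomized patients". That phrase opens the sentence introducing the random regression (HLM) models, and the argument that incomplete cases need not be dropped concerns those models. Directly after the logistic regression, the plan adds an HLM for dichotomous abstinence through the same follow-up. It then says that abstinence from each other drug will be analysed in parallel. The inclusion criteria require a screen negative for cocaine and for non-prescribed methadone or opiates.

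For the logistic regression, no estimator, separation rule or missing-outcome rule is stated.

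**The concern.** Maximum-likelihood logistic regression is biased away from the null when the smaller outcome group has few people per parameter. If a covariate pattern predicts the outcome perfectly (separation), it gives no finite estimate. An open, data-driven covariate list at 20 per arm invites both problems.

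A single-visit regression also cannot use someone with no outcome at that visit unless a rule supplies one, which sits badly with a promise to analyse everyone randomised. At stake is the long-term abstinence estimate in a pilot whose data are meant to support an application for a larger trial.

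**Working it through.** **Plan's own figure.** There is none to reproduce. The documents give no abstinence rate, effect size, alpha or power for this analysis. All rates and effects below are assumptions.

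**Analysed N.** Data Quality Control expects follow-up above 90% through month 6: 40 × 0.90 = 36. Strictly above 90% means at least 37, so 36 is the lower edge of the range 36-40.

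**Bias.** I simulated 1,500 trials per scenario with 1:1 allocation, a true conditional odds ratio (OR) of 3, baseline sample OR 0.30 and any further covariates at OR 1.5 each. Bias = 100 × (ln of geometric-mean OR ÷ ln 3 − 1). For example, ln 3.43 ÷ ln 3 = 1.233 ÷ 1.099 = 1.12, or 12%. Monte Carlo error is about 2 percentage points. With 30% control abstinence:

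| Covariates besides arm | ML OR (bias), N = 36 | ML OR (bias), N = 40 | Firth OR, N = 36 / 40 |
|---|---|---|---|
| 0 | 3.28 (8%) | 3.27 (8%) | 3.05 / 3.05 |
| 1 (baseline sample) | 3.43 (12%) | 3.25 (7%) | 3.04 / 2.94 |
| 2 | 3.62 (17%) | 3.41 (12%) | 3.12 / 2.99 |
| 3 | 3.77 (21%) | 3.70 (19%) | 3.01 / 3.02 |
| 5 | 4.49 (37%) | 4.35 (34%) | 3.12 / 3.09 |

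At N = 36 the smaller outcome group averages 14.7 people for 2 parameters with one covariate (about 7 each), and 14.4 for 6 parameters with five (2.4 each). A second simulation, also with true OR 3, gave 11-13% bias with the one named covariate and 24-38% with four at 20-30% control abstinence. Firth bias there was 4% or less.

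**No true effect.** At N = 36, 30% abstinence and 1, 3 or 5 covariates, the mean OR was 0.98-1.01 and rejection at a nominal two-sided 5% was 3.7-4.2%.

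**Separation** (no convergence, or a coefficient above 12 in absolute value):

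- At 30% control abstinence and OR 3: about 1-3% of trials with 1 to 5 covariates. The second simulation gave 1-4% at 20-30%. With no true effect, fewer people are abstinent and it is 3-6%.
- At 10%: 24-35% in the first simulation and 14-23% in the second. Among fits that do converge with 1 to 3 covariates, bias is only −6% to +9%, because the extreme datasets have dropped out.
- Single-drug outcomes at an assumed 90-95% control abstinence, plausible for cocaine or opiates given the entry screen: 76-96% with 1 or 2 covariates at N = 36. Firth stays finite but shrinks the true OR of 3 to between 1.7 and 2.3.

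**Missing outcomes.** Suppose 6 abstinent are observed in control and 10 in active, with 4 of 40 outcomes missing. Unadjusted, attenders only:

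- All 4 missing in control: (10/10) ÷ (6/10) = 1.67.
- Two missing in each arm: (10/8) ÷ (6/12) = 2.50.
- All 4 missing in active: (10/6) ÷ (6/14) = 3.89.
- Missing coded as using: (10/10) ÷ (6/14) = 2.33 in every case.

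With 3 missing, the attenders-only range is (10/10) ÷ (6/11) = 1.83 to (10/7) ÷ (6/14) = 3.33.

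**The case against.** The strongest reply is that this is a gap in specification rather than a demonstrated error. Much of that stands, and it rules out several stronger readings that a reader might infer.

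- **That the plan uses several covariates.** One is named; the rest are possible, not specified. With that one the bias is modest, and close to the 8% seen with no covariates. In a further check with a true log-OR of 1.0 and about 7-13 events, the one-covariate mean was 0.97-1.12 against a median standard error of 0.76-0.95.
- **That false positives are inflated.** They are not; the bias needs a true effect.
- **That the model will often fail.** For any-substance abstinence at 20-30% it seldom would. The documents give no rate, so the higher figures are conditional.
- **That the plan drops missing participants.** The text is silent. Complete-case analysis is a software default, as is standard maximum likelihood. The companion HLM keeps people with partial data, and phone or mailed visits and the Timeline Follow-back may recover some outcomes.
- **That this odds ratio will size the next trial.** The plan says only that pilot data will support an application. The primary outcomes are longest duration of abstinence and PTSD symptoms, and the focus is the 10-week treatment period.

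The reply does not remove the point. The covariate list remains open, and the plan does not say whether the logistic model or the HLM leads. A phone or mailed follow-up also yields no urine or breath sample, so objective outcomes may be fewer than completed visits.

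**Conclusion.** The concern holds in a limited form, for a secondary analysis in a pilot. Under standard maximum likelihood, with a true OR of 3 and 20-30% control abstinence, the log odds ratio is too large by about 7-13% with the named covariate and about 20-40% with three to five. There is no type I error inflation. Separation is about 1-4% at those rates, about 14-35% at 10% abstinence, and likely in single-drug repeats where nearly everyone is abstinent. As written, the regression has no means of including participants without a follow-up outcome, and three or four such people can move the estimate materially. These sizes depend on assumed abstinence rates, covariate effects and estimator, none of which the documents state.

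**What to change.** Amend the long-term paragraph of Aim 3:

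1. Fit Firth penalised logistic regression with profile-likelihood 95% confidence intervals.
2. Fix the model in advance as treatment group and baseline sample result, optionally with gender as the other urn factor, in place of selection from observed baseline differences.
3. Report very sparse single-drug outcomes descriptively, by a threshold set in advance, because Firth shrinks noticeably there.
4. Handle missing follow-up outcomes by multiple imputation and state how intervals are pooled. Give attenders-only and missing-as-using results as sensitivity analyses.
5. Report the dichotomous HLM separately, since its subject-specific odds ratio is a different quantity, and say which of the two leads.
6. Name the visit. The same section speaks of both a 3-month follow-up and a 3-month post-treatment follow-up, while the schedule has 3- and 6-month visits.

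The cost is wording and standard software, with slight shrinkage outside the sparse outcomes and fewer covariates. Priority is below the primary analyses.
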